9.3 Treatment assignment

Subjects who have been found to comply with all the inclusion criteria and not to violate any of the exclusion criteria will be randomised at baseline (Day 0) to receive treatment with either tralokinumab or placebo in the initial treatment period. Treatment assignment will be pre-planned according to a computer-generated randomisation schedule in a 3:1 ratio (tralokinumab:placebo) stratified by region (North America, Japan, and Europe) and baseline disease severity (IGA 3 or 4).

Subjects found to be eligible for maintenance treatment at Week 16 will be re-randomised to the maintenance treatment period in a 2:2:1 ratio (tralokinumab Q2W:tralokinumab Q4W:placebo) stratified by region and IGA response at Week 16 (IGA 0/1 or IGA >1).

Subjects randomised to placebo in the initial treatment period who achieve a clinical response at Week 16 (IGA 0/1 or EASI75) will continue to receive placebo Q2W in the maintenance treatment period.

Trial ID: LP0162-1325	Date: 14-Aug-2018	Version: 4.0
		Page 56 of 169

Subjects not eligible for the maintenance part of the trial will be transferred to open-label tralokinumab Q2W treatment.

IWRS will be used to control randomisation and stratification factors, along with IMP supply chain and expiry tracking.

9.3.1 Blinding

This is a double-blinded trial in which tralokinumab and placebo are visually distinct from each other. Neither the subject nor any of the investigator or LEO staff who are involved in the treatment or clinical evaluation and monitoring of the subjects will be aware of the treatment received. The packaging and labelling of the IMPs will contain no evidence of their identity.

Since tralokinumab and placebo are visually distinct and not matched for viscosity, IMP will be handled and administered by a qualified, unblinded HCP at the site who will not be involved in the management of trial subjects and who will not perform any of the assessments.

In the event that the treatment allocation for a subject becomes known to the investigator or other study staff involved in the management of trial subjects, LEO must be notified immediately.

Should an issue arise with the IMP (e.g., damaged kit or syringe that has been assigned to a subject prior to administration, or any other unexpected event with the kit or syringe [e.g., a malfunction during IMP administration]), the unblinded HCP at the site will contact the clinical research associate (CRA) to determine whether any specific actions are required.

The trial site will maintain a written plan detailing which staff members are blinded/unblinded and the process of IMP administration used to maintain the blind.

9.3.2 Emergency unblinding of individual subject treatment

While the safety of a subject always comes first, it is still important to carefully consider if unblinding is necessary to ensure a subject's safety. An emergency unblinding request can be made by the investigators, HCPs who are not members of the trial staff, or authorised LEO personnel.

Provisions are in place for 24 hour emergency unblinding of individual subject treatment. If emergency unblinding is required, the investigator can unblind a subject's treatment in the

Trial ID: LP0162-1325	Date: 14-Aug-2018	Version: 4.0
		Page 57 of 169

IWRS. For a requester who is not a member of the trial staff and who does not have access to the IWRS (e.g., a physician at an emergency room), a local contact number for the emergency unblinding contract research organisation (CRO) is provided on the subject card (see Appendix 4B) to be used if the investigator or delegated site staff cannot be reached. The requester will provide the trial ID and subject ID to the emergency unblinding CRO who will immediately reveal the individual treatment allocation.

The emergency unblinding CRO will clarify that the requester requires immediate unblinding without further medical consultation. Should the requester wish to discuss whether unblinding is necessary, the emergency unblinding CRO will provide the requester with the LEO 24/7 contact which will be diverted to the medical cover.

9.4 Background treatment (emollients)

All subjects must use an additive-free, basic bland emollient twice daily (or more, as needed) for at least 14 days before randomisation. Subjects are not allowed to start treatment with prescription emollients or emollients containing additives such as ceramide, hyaluronic acid, urea, or filaggrin, unless initiated prior to the screening visit (Section 9.6). Subjects must continue their background emollient treatment throughout the trial.

9.5 Concomitant medication and procedures

Any medication or vaccine that the subject receives from 3 months prior to screening through safety follow-up (FU1 [Week 66] or FU2 [Week 82]) must be recorded in the subject's medical record and the eCRF along with details such as:

- Reason for use.
- Dates of administration including start and stop dates.
- Dosage information including dose and frequency.
- For topical treatments: size of treated area ($\leq 250 \text{ cm} 2 \text{ or } > 250 \text{ cm} 2$).

Similarly, concomitant procedures (including body location, diagnosis, and start and stop date) must also be recorded in the subject's medical record and the eCRF. Note: in this trial, only surgical procedures will be recorded.

Investigators may prescribe concomitant medications or treatments to provide adequate supportive care as deemed necessary, except for medications listed in Section 9.6. The

Trial ID: LP0162-1325	Date: 14-Aug-2018	Version: 4.0
		Page 58 of 169

sponsor's medical expert should be contacted if there are any questions regarding concomitant or prior therapy.

Concomitant medication for conditions other than AD may be continued throughout the trial without any change in dosage whenever possible.

The following concomitant medications related to AD treatment are permitted from screening through safety follow-up (FU1 [Week 66] or FU2 [Week 82]):

- Oral antibiotics, antiviral, or antifungal therapy for skin infections as appropriate.
- Stable doses of an emollient (see Section 9.4 for allowed emollients; subjects must apply such emollients twice daily [or more, as needed] for at least 14 days before baseline and throughout trial participation).
- Oral anti-histamines.

In addition, the use of topical treatments is permitted during safety follow-up (from Week 52 or Week 68) at the investigator's discretion.

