9.6 Prohibited medication and procedures

The following medications are prohibited during the trial from randomisation through Week 52 (or Week 68):

- TCS of any WHO class (except for subjects in open-label treatment).
- Other topical medications used for the treatment of AD, such as TCI.
- Use of ultraviolet A or B (UVA or UVB), psoralen + UVA (PUVA), other phototherapy, or tanning beds.
- Prescription emollients or emollients containing additives such as ceramide, hyaluronic acid, urea, or filaggrin (unless treatment was initiated prior to screening).
- Three or more bleach baths per week.

Any prohibited topical treatments must be recorded as concomitant medication.

The following medications are prohibited during the trial from randomisation through safety follow-up (FU1 [Week 66] or FU2 [Week 82]):

• Investigational agents other than tralokinumab

- Immunoglobulin or blood products
- Systemic corticosteroids (nasal and inhaled corticosteroids are allowed)
- Systemic treatment for AD with an immunosuppressive/ immunomodulating agent (e.g., cyclosporine, mycophenolate mofetil, azathioprine, methotrexate, Janus kinase inhibitors, interferon-gamma, or other biologics)
- Allergen immunotherapy
- Live (attenuated) vaccine

The sponsor's medical expert must be notified if a subject receives any of these medications during the trial.

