12.2 Trial analysis sets

All screened subjects will be accounted for in the CTR.

Trial ID: LP0162-1325	Date: 14-Aug-2018	Version: 4.0
		Page 92 of 169

All subjects randomised to initial treatment are included in the full analysis set and will be analysed for efficacy up to Week 16 (visit 12). Exclusions from the full analysis set can be considered in special cases as described in ICH E9, Section 5.2.1, Full Analysis Set. If it is decided to exclude a randomised subject from the full analysis set, a justification addressing ICH E9 will be given.

A per protocol analysis set will be used as an efficacy subset for the analysis of the primary endpoints up to Week 16 (visit 12), and analyses based on the per protocol analysis set will be performed to support the results obtained for the full analysis set. The per protocol analysis set will be defined by excluding subjects from the full analysis set for whom any of the following conditions apply:

- Receive no treatment with the IMP.
- Provide no assessment of IGA or EASI following start of treatment.
- Are known to have taken the wrong IMP throughout the initial treatment period of the trial.
- Do not fulfil all the inclusion criteria no. 3, 6, 7 and 8.

A maintenance analysis set will be defined as all subjects who receive tralokinumab in the initial treatment period and who are re-randomised to maintenance treatment.

A safety analysis set will be defined by excluding subjects from the full analysis set who either received no treatment with IMP and/or for whom no post-baseline safety data are available.

A maintenance safety analysis set will be defined as subjects in the full analysis set who are re-randomised to maintenance treatment at Week 16 (visit 12) and who have safety data available after Week 16.

An open-label safety analysis set will be defined as subjects in the full analysis set who are still in the trial at Week 16 (visit 12), who have safety data available after Week 16 and who at any point in time enter the open-label treatment arm.

Based on the above-mentioned rules, the inclusion/exclusion of subjects from the trial analysis sets will be documented in the statistical analysis plan update before breaking the randomisation code.

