12.3.6 Analysis of maintenance treatment

12.3.6.1 Analysis of maintenance endpoints

For the two dichotomous maintenance endpoints, IGA 0/1 and EASI75 at Week 52, an adapted version of the primary estimand for the primary endpoints will be considered:

• Treatment difference in response rates of IGA 0/1 and EASI75 after 52 weeks achieved without rescue medication and without transfer to open-label treatment

The adapted estimand takes into account that throughout the maintenance period subjects will be actively discontinued from the treatment randomised at Week 16 and transferred to the open-label tralokinumab arm if they meet the prespecified treatment failure criteria described in Section 7.1.

This estimand assesses the expected difference in response rates (defined as response obtained without initiation of any rescue medication and without transfer to open-label treatment) after 52 weeks in patients responding to tralokinumab at Week 16 (as measured by a positive IGA 0/1 or EASI75 response), resulting from a maintenance treatment regimen with tralokinumab Q2W or tralokinumab Q4W compared to a treatment regimen with placebo.

Primary analysis for the maintenance estimand

All subjects who prior to the Week 52 visit have received rescue medication, including TCS, and/or been transferred to the open-label tralokinumab arm will be considered non-responders.

This reflects an assumption that initiation of rescue medication or transfer to open-label treatment indicates failure of the re-randomised treatment assigned at Week 16, and that a (possible) observed positive response thereafter is not attributable to the treatment received from Week 16. In addition, all subjects with missing endpoint data at Week 52 visit will be imputed as non-responders.

Trial ID: LP0162-1325	Date: 14-Aug-2018	Version: 4.0
		Page 109 of 169

The 4 hypotheses of primary interest for maintenance treatment will be tested sequentially with the next hypothesis in the sequence only being tested if the previous one was significant. The multiple testing procedure planned to control the overall type 1 error rate for the trial is described in detail in Section 12.3.4. The maintenance endpoints will be evaluated in the following order:

- No difference between Q2W and placebo for IGA 0/1 at Week 52.
- No difference between Q2W and placebo for EASI75 at Week 52.
- No difference between Q4W and placebo for IGA 0/1 at Week 52.
- No difference between Q4W and placebo for EASI75 at Week 52.

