# 6.3 Rescue medication

Rescue medication is defined by the following algorithm: Concomitant medications with Dermatitis atopic or Dermatitis infected as the preferred term for the indication and either ATC2 code H02 or D07, or ATC4 code D11AH or Preferred name Methotrexate, Ciclosporin, Azathioprine, Mycophenolate-mofetil, Mycophenolate-sodium, Mycophenolate-acid or Dupilumab.

According to the protocol investigators should make every attempt to conduct efficacy and safety assessments immediately before administering any rescue treatment. Therefore, if rescue medication has start date the same day as an efficacy assessment, then the assumption will be that the assessment is not influenced by the rescue medication, see also Section 6.8.4.

Rescue medication will be summarised separately for the initial and maintenance period. In addition, a summary table of rescue medication by type (topical and systemic) and by overall group (corticosteroids, immunosuppressants and other) will be made.

For subjects continuing with maintenance or open-label treatment at Week 16, the table of rescue medication during initial treatment period will include rescue medication taken (but not necessarily initiated) between the first dose of initial treatment and the first dose of either maintenance or open-label treatment. For subjects who do not continue with maintenance or open-label treatment, the table of rescue medication during initial treatment period will include medications taken after the first dose and before the (nominal) Week 16 visit (or before day 7\*16=112 after first dose, in case the (nominal) Week 16 visit did not take place).

The table of rescue medication during the maintenance treatment period will include rescue medication taken (but not necessarily initiated) after the first maintenance dose and exclude rescue medication initiated during the follow-up period.

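### UV and phototherapy have no required eCRF treatment field and lie outside the SAP rescue algorithm, so a subject given phototherapy for AD can be counted as a rescue-free responder

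*Protocol*

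**What the plan says.** **Recording.** Protocol 9.5 requires in the eCRF "Any medication or vaccine that the subject receives from 3 months prior to screening through safety follow-up". For procedures it adds a restriction: "in this trial, only surgical procedures will be recorded".

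**Prohibition.** Exclusion criterion 5 in section 8.3 sets a 6-week washout for tanning beds and phototherapy. The washout is 4 weeks for systemic immunosuppressants and 2 weeks for TCS and TCI. From randomisation through Week 52 (or 68), section 9.6 prohibits "Use of ultraviolet A or B (UVA or UVB), psoralen + UVA (PUVA), other phototherapy, or tanning beds". The recording duty that follows that list is narrower: "Any prohibited topical treatments must be recorded as concomitant medication". The duty in 9.6 to notify the sponsor's medical expert follows a second list, and phototherapy is not on it.

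**Rescue flag.** SAP 6.3: "Rescue medication is defined by the following algorithm: Concomitant medications with Dermatitis atopic or Dermatitis infected as the preferred term for the indication", combined with "ATC2 code H02 or D07, or ATC4 code D11AH or Preferred name Methotrexate, Ciclosporin, Azathioprine" and a few further drug names. Procedures are not a source, and no phototherapy or UV entry is on the list.

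**Use of the flag.** Protocol 12.3.5.1.1 makes a subject with rescue before Week 16 a non-responder. Section 12.3.6.1 defines maintenance response as "response obtained without initiation of any rescue medication and without transfer to open-label treatment". The hypothetical analyses (12.3.5.1.2 and 12.3.5.2.1) drop data collected after rescue starts. The per protocol set in 12.2 has four exclusions. One of them is "Do not fulfil all the inclusion criteria no. 3, 6, 7 and 8", and none concerns prohibited treatment.

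**The concern.** The protocol handles UV and phototherapy alongside TCS and TCI, as something to wash out and keep out. Section 9.6 gives no reason, but the natural reading is that these treatments can change the AD assessments. A subject who uses TCS during blinded treatment becomes a non-responder. A subject who has phototherapy for the same flare does not, because the derivation has nothing to act on.

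What is at stake is whether the responder classification means what the estimand says, and whether any cases are handled by a rule fixed in advance. The maintenance period is the more exposed part. It lasts 36 weeks, its placebo arm is small, and the transfer criteria in section 7.1 can leave a partly relapsing subject on blinded treatment. For example, a subject with IGA 1 at Week 16 transfers only after IGA of at least 3 without EASI75 over three consecutive visits, and not before Week 22.

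**Working it through.** **Step 1: trace one case.** Take a randomised subject who has a course of phototherapy for AD, takes no listed drug, and has IGA 0/1 or EASI75 at the endpoint visit.

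| Rule | Does it catch the case? |
|---|---|
| Protocol 9.5, procedures | No: not surgical |
| Protocol 9.5, medications | Not required: phototherapy is not a drug (the psoralen in PUVA is) |
| Protocol 9.6, recording duty | No: not topical |
| SAP 6.3, rescue algorithm | No: medication records and listed codes only |
| 12.3.5.1.1, composite, Week 16 | Non-response only for rescue or missing data: counted as responder |
| 12.3.6.1, maintenance, Week 52 | Non-response only for rescue, open-label transfer or missing data: counted as responder |
| 12.3.5.1.2 and 12.3.5.2.1, hypothetical | Exclusion follows rescue or IMP discontinuation only: data after phototherapy are kept |
| 12.2, per protocol set | Not excluded |

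Time to relapse (12.3.6.2.1) counts initiation of rescue medication as an event, so it has the same gap.

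**Step 2: reproduce the planned power.** Inputs are from protocol 12.1. The method is the pooled-variance normal approximation, two-sided.
- IGA 0/1 at Week 16, 585 vs 195, 30% vs 10%, 5% level: 99.9997%.
- EASI75 at Week 16, 40% vs 15%: above 99.9999%.
- IGA at Week 52, 4% level, placebo n=35 at 5%: Q2W (n=70, 80%) about 100%; Q4W (n=70, 50%) 99.98%.
- EASI75 at Week 52, 4% level, placebo n=47 at 5%: Q2W (n=94, 90%) about 100%; Q4W (n=94, 55%) above 99.99%.

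The stated >99% is reproduced throughout.

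**Step 3: weight of one case.** Points per subject = 100/n.
- Maintenance IGA placebo: 1/35 = 2.9 points. The expected count is 0.05 × 35 = 1.75, about 2 responders (2/35 = 5.7%).
- Initial placebo: 1/195 = 0.5 points.
- Initial tralokinumab: 1/585 = 0.2 points.

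**Step 4: range under assumed use.** The documents give no rate, so these are assumptions.
- Maintenance: 1 to 3 extra placebo responders give 3/35 = 8.6% to 5/35 = 14.3%. Fisher's exact test of 5/35 against the planned Q4W count of 35/70 gives p = 0.0005. At 10/35, p = 0.0396, still below 4%. At 11/35, p = 0.095. Nine placebo responders beyond the expected two would be needed before Q4W missed the 4% level.
- Initial period, opposite direction: suppose phototherapy-treated responders became non-responders and made up 0 to 10% of the tralokinumab arm and 0 to 5% of the placebo arm. The IGA difference would then run from 20% − 10% = 10 points to 30% − 5% = 25 points. Power is at least 99.8% with up to 5 points lost from tralokinumab, and 92.2% with 10 points lost from tralokinumab and none from placebo.
- Starting from 176/585 vs 20/195, tralokinumab would have to fall to 93/585 (15.9% vs 10.3%, z = 1.94) to lose significance at 5%. That means 176 − 93 = 83 reclassified responders.

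**The case against.** **Phototherapy may reach the database.** Section 9.6 lists UV under prohibited medications, so a site might enter it as one. Psoralen is a drug and falls under 9.5. The AE form in 11.2 allows a concomitant procedure as the action taken. Appendix 4D has deviations documented and included in the trial report. This stands. A reader might infer that such use can never be found or corrected, and the documents do not support that. But none of these routes feeds the responder derivation.

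**The estimand says without rescue medication.** A reader might infer that it promises response free of any other AD treatment. It does not. Section 9.5 permits oral antihistamines and oral anti-infectives with no consequence for response, and 9.7 describes rescue as topical or systemic medication. This also stands. Whether a prohibited non-drug treatment counts as rescue in the analysis is a definition that the sponsor has to state. The gap is that neither document states one.

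**Section 9.5 is not the whole cause.** Correct. Even if phototherapy were recorded as a procedure, SAP 6.3 would not read it.

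**The chain is unlikely and harmless.** The subject must receive a prohibited treatment without any listed drug, although 9.7 steers rescue to topicals first. In maintenance the subject must also avoid transfer, and in either period must respond at the endpoint visit. The frequency may well be very low, and the calculations show that the planned conclusions would survive. That limits the importance of the point but does not supply the missing rule.

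**Conclusion.** The gap is real. Following 9.5, 9.6 and SAP 6.3 exactly, a subject given phototherapy for AD who meets IGA 0/1 or EASI75 at Week 16 or Week 52 is analysed as a rescue-free responder, and the hypothetical analyses keep the data collected afterwards. Each case is worth 2.9 points in the planned IGA maintenance placebo arm, 0.5 points in the initial placebo arm and 0.2 points in the initial tralokinumab arm.

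A reader might infer that the error shrinks the treatment effect, because need is greatest on placebo, or that it threatens the result. The documents support neither. They give no rate of use in any arm. Use mainly by placebo responders would shrink the observed difference, and use mainly by tralokinumab responders would inflate it. Power is not in question under any assumption tried short of reclassifying 10% of the tralokinumab arm, where it is still 92.2%.

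The point therefore concerns correct classification and a fully specified estimand. It rests on the documents as they stand. Site instructions or eCRF guidance not included in them could require more.

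**What to change.** 1. Reconcile protocol 9.5, 9.6 and 9.7 with SAP 6.3, so that UV, phototherapy and tanning-bed use are recorded with type, indication, and start and stop dates. This adds one entry type to the existing procedures form.
2. Add to SAP 6.3 that phototherapy for AD after first dose is handled as rescue in the responder derivation, with the same date conventions as rescue medication (SAP 6.3 and 6.8.4). Handle any other UV or tanning-bed use the same way in a sensitivity analysis. This is an analysis rule only and does not change what subjects may receive. Steps 1 and 2 are both needed, since recording alone would leave the flag unchanged.
3. For subjects already treated, search deviations, medication records and AE forms blind to treatment, and fix the list of cases before unblinding. The SAP is dated 20-May-2019 and gives a data cut-off of 11 April 2019, so a change to 9.5 alone cannot recover initial or maintenance data. Protocol 12.3.10 already provides for review of the planned analyses against blinded data. If no cases are found, one sentence in the trial report closes the matter.

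The cost is slight extra data entry, one blinded review and possibly a few fewer responders. No visit or assessment is added. The retrospective search is only as complete as those three sources.
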